APPENDIX 5: GENERAL INSTRUCTIONS FOR INTERVENTIONISTS

- 1) To schedule telehealth visits with the PCPs, call [name]. These visits will be conducted via MyChart. Note that this does not apply if the participant does not have a Jefferson PCP.
- 2) To schedule telehealth visits with [name], contact her directly.
- 3) The audio recorder should not be on during the telehealth visits.
- 4) If you give the participant a mental health referral, please inform the PCP ASAP, and let them know where you sent the participant for care.
- 5) Please turn in all paperwork from the initial 6 sessions to the Study Coordinator within 2 weeks of the 6th session. Please enter the paperwork in REDCap and turn in any hard copies. Please turn in paperwork from the booster sessions within 2 weeks from each booster session. Tapes should be posted within 1 business day of the session being completed. The Study Coordinator will document that the paperwork was handed in, and it will then be scanned (and stored on the shared drive).

[figure not shown]
APPENDIX 6: PROCEDURES FOR RECORDING INCIDENT ED VISITS/HOSPITALIZATIONS

- 1) Whenever any staff learn of a new ED visit or hospitalization, they must complete an Incident Hospitalization/ED Visit Form. If the event was learned of at an assessment visit (baseline or FU), the Outcome Assessor will complete the required fields on the assessment in REDCap AND will complete an Incident Hospitalization/ED Visit Form in hard copy (not REDCap).
- 2) The completed Incident Hospitalization/ED Visit Form must be emailed to [name], [name], and [name] as soon as possible.
- 3) If the event occurred at Jefferson, [name] will go into EPIC and verify (and correct if necessary) the information on the Incident Hospitalization/ED Visit Form (for example, incorrect date).
- 4) If the event occurred at a non-Jefferson facility, [name] will fax the release and a request for details about the event to the treating hospital. Once the requested information is received, [name] will verify (and correct if necessary) the information on the Incident Hospitalization/ED Visit Form.
- 5) [name] will enter the verified and corrected data from the Incident Hospitalization/ED Visit Form into REDCap.
- 6) [name] will complete Part 1 of the Event Form and email to [name], [name], [name], and Drs. [name] and [name].
- 7) Drs. [name] and [name] will separately complete Part 2 of the Event Form, and email back to [name], [name], and [name].
- 8) If there is a discrepancy between the responses to Part 2 provided by Drs. [name] and [name], [name] will email the Event Form to [name] to complete. When there is not a majority determination among the 3 physicians, the 3 physicians will be asked to discuss the event and reach consensus.
- 9) [name] will enter each physician's response to Part 2 of the Event Form in REDCap.
- 10) Staff will conduct medical chart reviews for all participants at 6 and 12 months. If when reviewing the charts, staff learns of an ED visit or hospitalization that HAS NOT BEEN PREVIOUSLY reported by staff (i.e., an event for which there is no Incident Hospitalization/ED Visit Form), staff will complete an Event Form, and follow steps 6 through 9. In this situation, an Incident Hospitalization/ED Visit Form will not be completed.

[figure not shown]
APPENDIX 7: PROCEDURES FOR CHECKING DATA

[name] will check data via REDCap rather than SPSS. She will also make all edits in REDCap. [name] will download the SPSS files monthly. Procedures for checking data in REDCap are as follows.

[figure not shown]
- 1) Log on to REDCap.
- 2) Under "My Projects", click "PREVENT: Data".
- 3) Click "Add/Edit Records".

[figure not shown]
4) Find the subject from the drop down menu under "Choose an Existing Record ID". You will know when an assessment is complete because the assessor will send you an email, and the A1c print out will be attached to the email.

[figure not shown]
5) Go to the assessment that you want to review. Click on the first instrument for that assessment. Click on the red circle to open it.

6) Here you will see the responses to the first instrument.

7) When you get to the end of the instrument and all errors have been corrected, click "Complete" from the drop down menu. Then click "Save and Go to Next Form".

[figure not shown]
8) If you notice an error in the data, make the change in REDCap before you mark the instrument as "Complete". Log the change in the excel file called "Assessment Check", which will be stored on the shared drive. You can click on the "Instructions" tab in the excel file for instructions on how to complete this file. If there is an error (or missing data) that requires input from the Outcome Assessor, please send a data query to the Outcome Assessor using Data Query Table format depicted below. Please copy [name] and [name] on the email.

Data Query Table

Participant ID:	CRJC00001
Assessment date:	9/14/18
Assessment:	Part 2 Baseline
Data issue:	PHQ6 is blank and is not asked on the tape

Do not mark the instrument as "Complete" until the data query is resolved. Enter all data queries in the "Assessment Check" Excel file.

9) Once the entire assessment has been checked and everything is marked "Complete", download a pdf of the assessment. Label the pdf file with the subject's ID, assessment type, and date (for example, CRJC00001 6 MONTH 10-31-18). Save the pdf to the appropriate location on the shared. Save the image of the A1c result in the same folder on the shared.

APPENDIX 8: PROCEDURES FOR RECORDING ATTRITION AND MISSED VISITS

- 1) Study Withdrawal Form: [name] or [name] will complete this form when a participant drops out of the study, expires, or is no longer able to be reached.
- 2) Missed Visit Log: There will be 2 versions of this form: one for intervention/telehealth visits, and one for assessment visits. This form is to be completed by the Outcome Assessor or CHW interventionist every time a visit is missed, even if the visit is re-scheduled. For example, if there is a visit scheduled for 1/1/18, but the participant calls to request to change the visit to 1/3/19, the visit scheduled for 1/1/9 should be entered in the log. These REDCap forms are the Interventionist Missed Visit Form and the Assessor Missed Visit Form.
- 3. Out of Window Log: There will be 2 versions of this form: one for intervention/telehealth visits, and one for assessment visits. This form is to be completed every time a visit is out of window as per the schedule of visits provided by [name]. These REDCap forms are the Assessor OOW Log and the Interventionist OOW Log.

To keep track of the number of times that staff are attempting to reach participants, staff will be asked to maintain a call log in REDCap for each participant that tracks the date of each time staff called or attempted to call the participant. The Outcome Assessor will use the Assessor Communication Log, and the CHW Interventionists will use the Interventionist Communication Log.

[figure not shown]
APPENDIX 9: POSTING DOCUMENTS TO EPIC

To Upload Documents

- 1. Sign into Epic
- 2. Click on "Pt Research Studies"

3. Enter MRN number for patient and Select "Find Patient"

Please note that if you've already searched for this patient, they will be listed under the "Recent Patients" tab

- 4. Confirm that this is the correct patient, and double click on highlighted name
- 5. Click on Epic button

[figure not shown]
6. Click on Media Manager

[figure not shown]
- 7. Double click on highlighted patient name
- 8. Click on scan

[figure not shown]
9. Click in top left of black bar and select "File"

[figure not shown]
10. Click import file

[figure not shown]
- 11. Click on "This PC"
- 12. Click on Local Disk C: drive (Note: yours will have your PC# listed)

[figure not shown]
13. Click on "Users"

14. Click on your campus key folder

15. Click on location where you saved your document

Note: I save any document that I will be posting to Epic on my Desktop for ease of upload

[figure not shown]
16. Next to file name, make sure that PDF is selected

- 17. Search and select file
- 18. Form will show up in preview window

[figure not shown]

- 19. Under "Store image as" section click on "Choose document type"
 - a. Either scan black and white or scan color
- 20. Document type: Research Document
- 21. Document Description: Research Document 17S.027 (JT 10407)

22. Click "OK"

23. Click "Upload Images"

[figure not shown]

24. Close out of Media Manager

25. Click on "Chart Review"

26. Click on the "Media" tab

[figure not shown]
27. Click on the document that you just uploaded

28. Click on "Route"

[figure not shown]
- 29. In "Cover Page Message" type:
 - a. CHW: Please see attached for research document re: study 17S.027. Study visit conducted by on .
 - b. [name]: Please see attached for research document re: study 17S.027. Study visit conducted by [name], DNP, CRNP, CDE on _____.
- 30. Click "Add" button
- 31. Enter Study Team (as applicable: [name], [name], [name](these 3 always), PCP, [name], CHW ([name] or [name]))

[figure not shown]
32. Click "Send"

To View Documents Uploaded

1. A message will be sent to the recipients as a CC'd Chart

2. Click on patient name and the message will pop up with a link to the document

3. Click on link to view document

To Delete Documents Uploaded Erroneously

- 1. Under Media Manager, click on document to be deleted.
- 2. Double click on the scanned document
- 3. Click on the blue button "Send to Document Corrections"
- 4. A window will open where you can indicate what you want done
 - a. Ex. Please delete scan"
- 5. Then click on the save button

This will submit the request to HIM for them to delete.

APPENDIX 10: INTRUCTIONS FOR THE OUTCOME ASSESSOR TO COMPLETE THE DATA SHEET FROM BASELINE PART 1 IN PARTICIPANTS' HOMES

- Prior to the B1 visit, you will receive the participant's:
 - Current medications
 - Current medical conditions
 - Past medical conditions
 - Outpatient visits in past 6 months
- You should take the following with you to confirm with the subject:
 - Current medications
 - Current medical conditions
 - I recommend reviewing before the visit, as the subject may not be aware of some of the medical terms
 - Past medical conditions

Hospital bed #:

- I recommend reviewing before the visit, as the subject may not be aware of some of the medical terms
- Please fill out the Datasheet as you normally do. You will skip the following questions ([name] will enter them directly into REDCap Datasheet):
 2. AA should identify ED clinician team: Resident _____ Attending _____
 5. AA should record patient's (from Epic) Height: _____ inches & Weight: _____ pounds
 6. AA should record intake vitals (from Epic) SBP: _____ mmHg DBP: _____ mmHg
 7. Documented ED Arrival Date and Time: _____ (HH:MM): _____
 8. Documented ED Triage Date and Time: _____ (HH:MM): _____
 9. Study Screen Date (MM/DD/YYYY): _____
 10. Study Screen Number: _____
 16. Patient's health insurance provider and plan (check insurance card):
 29. Left Main ED Date & Time (MM/DD/YYYY): (HH:MM):
- 31. List ED final diagnoses below:

 ED Final Diagnoses

 ICD10 Codes

•	Document the medication/medical condition confirmation on the	the Enic nrint outs	To save time while in
•	Document the inedication/inedical condition committation on	uic Epic print outs.	10 30 VC tillic Willic III

the home, you will enter this information directly into REDCap Datasheet when you're back in the

30. Patient disposed to: ☐Home ☐Obs Unit ☐☐Inpatient ☐Transfer ☐Other:

- NOTE: If there is a self-report medication change/addition, this info should be documented in
 - NOTE: If there is a self-report medication change/addition, this into should be documented in REDCap Baseline Part 2.
- As part of Baseline Part 2, you should ask about any visits in the past 6 months.
- Once you're back in the office, you should enter the Epic print out into Datasheet.

• This may seem redundant, but Epic may not capture out of network visits, so any self-reported visits should be entered into Baseline Part 2.

APPENDIX 11: INSTRUCTIONS FOR PHARMACY REFILL DATA

All patients: The assessor will be getting pharmacy information from participants' diabetes medication bottles at each assessment time wave (baseline, 6M and 12M)

a. This information is gathered on the "Vitals/HbA1c" form

*Jefferson Patients

- 1. *Jefferson Patients- We will also check Epic for Jefferson patients to insure that we have all pharmacies on file
 - a. Log into Epic
 - b. Search Subject by MRN
 - c. Look up pharmacy information indicated in subject's chart.
- 2. *All Patients- Print out pharmacy refill release form from shared drive
- 3. Write in pharmacy information
 - a. Name
 - b. Phone
 - c. Fax
- 4. Print out pharm release cover form from Filemaker
 - a. In Filemaker
 - i. Click "Find" and search subject's ID
 - ii. Change layout (top left) to PHARMACY RELEASE FORM 6M or 12M
 - iii. Click "Preview"
 - iv. Click "Print Setup"
 - 1. Select "Landscape"
 - v. Click "Save as PDF"
 - vi. Will need to edit time frame (in bold)—should be date of baseline assessment (oldest pharm refill doc) through date of 6M or 12M assessment (newer pharm refill doc)
 - 1. Click "Tools"
 - 2. Click "Edit Text & Images"
- 5. Fax both docs to PCP (sub signed release form and release form cover (from FM))
- 6. Once you receive the records back from the pharmacy, write study ID and save on the shared drive folder: under the subject's folder in the Assessment PDF and tapes folder
- 7. Enter information into REDCap
- 8. File paper copies in chart 1.

APPENDIX 12: INSTRUCTIONS FOR CHART CHECKS

Jefferson Patients:

- 1. Log into Epic
- 2. Search Subject by MRN
- 3. Take a screen shot (use Snipping Tool) of the following items:
 - a. Outpatient visits
 - Epic- Chart review- all visits between Recruitment Visit/6M Review Date and 6M/12M Assessment
 - b. Problem list
 - i. Epic- Snap shot
 - c. Medical history
 - i. Epic- Snap shot
 - d. Medications
 - i. Epic- Chart Review- Meds (include all meds taken between Recruitment Visit/6M Review Date and 6M/12M Assessment
- 4. Convert jpeg docs into PDFs
 - a. Add subject initials, ID, date of review and your ID to each page
- 5. Save the PDFs on the shared drive folder: under the subject's folder in the Assessment PDF and Tapes folder (Neurology_ DM_I-Team -> DM ITEAM-CLINICAL TRIAL -> ASSESSMENT PDFS & TAPES)
 - a. Save to subject's folder:
 - i. Save file as: SUB INITIALS ID ASSESS CHART CHECK DATE
 - 1. i.e. EDJMM00002 6M CHART CHECK 6-28-18
- 6. Print out Medical History and Problem List pages and give to [name]
 - a. [name] will circle the conditions to be entered into REDCap
- 7. Scan these pages and replace the original pages in the chart check PDF
- 8. Enter information Into REDCap
- 9. Enter chart check/data entry dates to tracking file on shared drive
 - a. Neurology_DM_I-Team -> DM ITEAM-CLINICAL TRIAL -> CHART REVIEW BLANK->DM I-TEAM CHART REVIEW TRACKING (xls doc)

Non-Jefferson Patients:

- 1. Send signed med release to subject's PCP
 - a. Be sure patient's name and DOB is listed
 - b. Write in Physician's name
 - c. Under Specific Information to be released
 - i. Check off summary of records
 - ii. Covering the period(s) of treatment from _(date of med release)_ to _(date of 6M/12M assessment)
- 2. Once you receive the records back from the PCP's office:
 - a. Add subject initials, ID, date of review and your ID to each page

- Save the PDFs on the shared drive folder: under the subject's folder in the Assessment PDF and Tapes folder (Neurology_ DM_I-Team -> DM ITEAM-CLINICAL TRIAL -> ASSESSMENT PDFS & TAPES)
 - a. Save to subject's folder:
 - i. Save file as: SUB INITIALS ID ASSESS CHART CHECK DATE
 - 1. i.e. EDJMM00002 6M CHART CHECK 6-28-18
- 4. Give Medical History and Problem List pages and give to [name]
 - a. [name] will circle the conditions to be entered into REDCap
- 5. Scan these pages and replace the original pages in the chart check PDF
- 6. Enter information Into REDCap
- 7. Enter chart check/data entry dates to tracking file on shared drive
 - a. Neurology_DM_I-Team -> DM ITEAM-CLINICAL TRIAL -> CHART REVIEW BLANK > DM I-TEAM CHART REVIEW TRACKING (xls doc)

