Outcome Assessor, To be hired. The Outcome Assessor will administer Part 2 of the Baseline assessment and follow-up assessments at 6 and 12 months in participants' homes masked to treatment assignment. The Outcome Assessor will obtain informed consent and administer Part 1 of the Baseline Assessment to participants who do not want to be consented in the hospital. [name] will supervise the Outcome Assessor.

Study Coordinator, [name]. [name] will be responsible for providing assistance to [name] with the overall conduct of the PREVENT trial. In addition, she will assist [name] in managing study data. Specifically, she will: 1) maintain administrative data bases (e.g., participant contact information); (2) manage the payment of participant incentives; and (3) send biweekly reports to the Outcome Assessor and CHW Interventionists to inform them of participants who are due for follow-up assessments and intervention visits. Drs. [name] and [name] will supervise the Research Coordinator.

Research Assistant, To be hired. The Research Assistant will be supported by the Department of Neurology at Jefferson. This person will be responsible for: (1) reviewing participants' medical charts at 6 and 12 months to collect data on current medications, diabetes quality metrics, and recent hospitalizations and ED visits; and (2) listen to audiotapes of data collection visits for quality assurance purposes.

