Subjective Access to Care: We will use the Patient Satisfaction Questionnaire-18 (PSQ-18) to measure subjective perceptions of access to care (higher scores reflect better access). We will test PREVENT's efficacy to increase PSQ-18 scores (secondary outcome), and also determine if change in PSQ-18 scores mediates PREVENT's treatment effect (PSQ-18 as a mediator). This 18-item instrument has demonstrated reliability and validity, and includes 7 subscales: 1) General Satisfaction (e.g., "I'm dissatisfied with some things about the medical care I receive."); 2) Technical Quality ("I have some doubts about the ability of the doctors who treat me."); 3) Interpersonal Manner ("My doctor treats me in a very courteous and friendly manner."); 4) Communication ("Doctors are good about explaining the reasons for medical tests."); 5) Financial Aspects ("I have to pay for more of my medical care than I can afford."); 6) Time Spent with Doctor ("Doctors usually spend plenty of time with me."); and 7) Accessibility ("It's hard to get an appointment right away."). Responses are scored (1 to 5) in a "strongly agree/strongly disagree" Likert format. We will also examine change in the individual subscales.

Objective Access to Care: We will measure participants' receipt of up to five American Diabetes Association-recommended DM Quality Metrics as an objective indicator of realized access to care. The 5 metrics will be: twice yearly HbA1c testing (outside the research protocol), annual blood pressure check, urine protein testing, foot exam, and influenza vaccination. We will review medical records to identify receipt of these 5 metrics. Scores will range from 0 to 5, with higher scores reflecting better achieved access to the health system. We will test PREVENT's efficacy to increase the number of received DM Quality Metrics (secondary outcome), and also determine if change in

number of received DM Quality Metrics mediates PREVENT's treatment effect (DM Quality Metrics as a mediator). For each indicator, we will count them as having occurred if the date of the event is within 30 days in either direction of the due date.

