6.7. Medical chart review

Once a participant is randomized, staff will review participants' medical charts at baseline, 6, and 12 months, and will complete a standardized form to document current medications, medical diagnoses, health visits, lab tests and screens, and ED visits and hospitalizations.

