6.9. Schedule of Study Activities

Study activities will conform to the following schedule:

Screening: At the Index ED Visit

Part 1 Baseline assessment: Within 2 weeks of the Index ED visit Part 2 Baseline assessment: Within 2 weeks of the Index ED visit

Review baseline assessment: 1 week after Part 2 of Baseline Assessment

PI confirms eligibility: 1 week after Part 2 of the Baseline Assessment is

reviewed

Randomization: 3 days after eligibility is confirmed PREVENT or EUC treatment begins: 1 to 2 weeks after randomization

6 initial PREVENT or EUC treatment sessions: To be completed 4 months from baseline

6 month follow-up assessment: 6 to 7 months after randomization

3 booster PREVENT or EUC treatment sessions: 6 to 12 months after randomization

12 month follow-up assessment: 12 months after randomization

Medical chart reviews: 6 and 12 months
Pharmacy record reviews: 6 and 12 months

7: CERTIFICATION PROCEDURES

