13.1.1. Secondary Aims

- 1. Test the efficacy of PREVENT to increase perceived access to care over 12 months (secondary outcome). Hypothesis: PREVENT will increase Patient Satisfaction Questionnaire-18 (PSQ-18) scores to a greater extent than EUC over 12 months.
- 2. Test the efficacy of PREVENT to increase realized access to care over 12 months (secondary

outcome). Hypothesis: PREVENT will increase the number of received Diabetes Quality Metrics to a greater extent than EUC over 12 months.

3. Test the efficacy of PREVENT to improve DM self-care over 12 months (secondary outcome). Hypothesis: PREVENT will improve Diabetes Self-Care Inventory (DSCI) scores to a greater extent than EUC over 12 months.

Analyses: For Secondary Aims 1 – 3, we will model PSQ-18 scores, number of received Diabetes Quality Metrics, and DSCI scores as continuous variables to estimate average change in each of these three variables over time by treatment group. We will use mixed effects linear regression with fixed effects for time (baseline, and months 6 and 12), randomization assignment, and time by randomization interaction. A random intercept term and an appropriate covariance structure will be used to account for correlation among repeated measurements. Within this model we will estimate the average change in PSQ-18 scores, number of received Diabetes Quality Metrics, and DSCI scores, respectively, by treatment group, from baseline to 6 months, from 6 to 12 months, and from baseline to 12 months. For each of these 3 Secondary Aims, the primary hypothesis will be tested by comparing the groups with respect to change from baseline to 12 months.

4. Determine if increasing subjective and/or objective indicators of access to care and/or DM self-care mediates PREVENT's reduction of DM-related ED visits and/or hospitalizations. Hypothesis: PREVENT will reduce DM-related ED visits and/or hospitalizations to the extent that it increases subjective and/or objective indicators of access to care and/or improves DM self-care.

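### Secondary Aim 2 tests change from baseline in the Quality Metrics score, but no look-back is defined for any time point and the record-retrieval periods do not support that contrast

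*Combined protocol and SAP*

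**What the plan says.** Section 13.1.1 (Secondary Aims) models the number of received Quality Metrics at baseline, month 6 and month 12 "to estimate average change in each of these three variables over time by treatment group". The hypothesis test is made by "comparing the groups with respect to change from baseline to 12 months". Change in the same score is also a candidate mediator under Secondary Aim 4.

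Section 6.2 (Objective Access to Care) scores five items from 0 to 5: "twice yearly HbA1c testing (outside the research protocol), annual blood pressure check, urine protein testing, foot exam, and influenza vaccination". An item counts if it is dated within 30 days either side of a due date, and no section defines that date.

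The documents disagree on when charts are reviewed:
- Section 6.7: "staff will review participants' medical charts at baseline, 6, and 12 months", with a form that records lab tests and screens. Table 5 likewise lists the Quality Metrics at baseline and follow-up.
- Section 6.9: "Medical chart reviews: 6 and 12 months".
- Section 3.2 gives the Research Assistant the task of "reviewing participants' medical charts at 6 and 12 months to collect data on current medications, diabetes quality metrics", with no baseline review.

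Appendix 12 sets the retrieval periods. For Jefferson patients the Epic visit check takes "all visits between Recruitment Visit/6M Review Date and 6M/12M Assessment". For non-Jefferson patients the request to the PCP is worded "Covering the period(s) of treatment from" the date of the medical release to the date of the 6M or 12M assessment. Section 6.1 has that release signed at Part 1 of the baseline assessment.

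**The concern.** A change score needs the same quantity measured at both ends. For items due once or twice a year, that means a look-back of about a year ending at baseline and another ending at month 12. The retrieval rules request no pre-recruitment year. They give a month-6 check too short for annual care, and a month-12 check whose literal length depends on who the participant's PCP is.

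Two things are at stake. First, whoever scores this outcome must choose the baseline window, the month-12 window and the due date, possibly after seeing data. Second, movement in the score over time can reflect window length instead of access to care. That affects the Aim 2 change and the Aim 4 mediator alike.

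**Working it through.** The documents give no SD, receipt rate, effect size or power for this score, so there is no figure of theirs to reproduce.

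**Step 1: periods retrieved, read literally**

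| Score | Jefferson PCP | Non-Jefferson PCP |
|---|---|---|
| Baseline | no look-back stated | no look-back stated |
| Month 6 | recruitment to 6M, about 6 months | release to 6M, about 6 months |
| Month 12 | 6M review date to 12M, about 6 months | release to 12M, about 12 months |

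The only dated pre-recruitment period in the appendices is in Appendix 10: outpatient visits in the past 6 months, for the Part 1 data sheet. That is too short for annual items.

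**Step 2: size of the window effect, care held constant**

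*Fully adherent participant (assumed).* Each of four annual items is received once a year at a random time, and HbA1c is tested every 6 months. A 12-month window scores 5. A 6-month window scores 4 × 0.5 = 2.0 if two HbA1c tests are still required, or 2.0 + 1 = 3.0 if one is enough. The shift is 5 − 3.0 = 2 to 5 − 2.0 = 3 points.

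*Constant-rate model (assumed).* Let p be the 12-month probability of each annual item and L the yearly HbA1c testing rate (Poisson), with two tests required in either window.
- 12 months: 4p + 1 − e^(−L)(1 + L)
- 6 months: 4[1 − (1 − p)^0.5] + 1 − e^(−L/2)(1 + L/2)

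| p, L | 12 months | 6 months | Shift |
|---|---|---|---|
| 0.5, 1.5 | 2.00 + 0.44 = 2.44 | 1.17 + 0.17 = 1.34 | 1.10 |
| 0.6, 2 | 2.40 + 0.59 = 2.99 | 1.47 + 0.26 = 1.73 | 1.26 |
| 0.7, 2 | 2.80 + 0.59 = 3.39 | 1.81 + 0.26 = 2.07 | 1.32 |
| 0.8, 2.5 | 3.20 + 0.71 = 3.91 | 2.21 + 0.36 = 2.57 | 1.35 |
| 0.9, 3 | 3.60 + 0.80 = 4.40 | 2.74 + 0.44 = 3.18 | 1.22 |

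The shift is about 1.1 to 1.35 points. If one HbA1c test were enough in 6 months, the last 6-month term becomes 1 − e^(−L/2). At p = 0.7, L = 2 the 6-month score is then 1.81 + 0.63 = 2.44 and the shift 0.95; over the five pairs it is 0.74 to 0.99.

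**Step 3: effect on the comparison between arms**

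*Bias from PCP mix* = imbalance in the Jefferson share × shift. An imbalance of 2 percentage points gives 0.02 × 1.32 = 0.026, and 5 points gives 0.05 × 1.32 = 0.066. PCP affiliation is a stratification factor (section 5.7), so imbalance should be small.

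*Noise from mixed month-12 windows* = √[f(1 − f)] × shift, where f is the Jefferson share. For f from 0.3 to 0.7 the added SD is about 0.50 to 0.66. Power with 78 per arm, an assumed difference of 0.5, two-sided alpha 0.05 (assumed) and added SD 0.6, so that total SD = √(SD² + 0.36):
- SD 1.0: 0.88 falls to 0.76
- SD 1.3: 0.67 falls to 0.59
- SD 1.5: 0.55 falls to 0.49

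This is an upper illustration. It ignores baseline and any PCP term; the Aim 2 model as written lists none.

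*Attenuation.* The six initial sessions and the PCP telehealth visit fall in the first four months (section 9.1). An annual test prompted at month 3 lies outside the literal Jefferson 6M-to-12M check but inside the non-Jefferson one. If care rates are instead raised by an assumed factor of 1.3 throughout, the arm difference is 0.51, 0.52, 0.50 and 0.43 over 12 months for the first four rate pairs, against 0.36, 0.43, 0.47 and 0.51 over 6 months. It shrinks in three cases and grows in one, so attenuation is possible but not certain.

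**The case against.** The strongest reply is that Appendix 12 is a retrieval checklist, not a scoring rule. It never names the Quality Metrics; for Jefferson patients it lists visits, problem list, history and medications. The scoring rule is the due-date rule in section 6.2. This stands in part: that the score is taken over 6 or 12 months is an inference from what is retrieved. But a due date that is never defined supplies no look-back, so the gap remains.

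A reader might infer that no valid baseline exists. The documents do not support that. Section 6.7 and Table 5 plan a baseline review and score, and Appendix 12 covers only the 6M and 12M checks. The baseline is inconsistently scheduled and has no stated period; it is not shown to be absent.

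A reader might also infer that no common month-12 value can be formed. That too goes too far. The two Jefferson checks are consecutive and together cover recruitment to month 12, apart from any days between the 6M assessment and the 6M review date. What is missing is an instruction to pool them.

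Finally, a reader might infer that the treatment contrast is biased. The retrieval periods do not depend on arm and PCP affiliation is stratified, so a window effect common to both arms cancels in the comparison. Even a month-12 level compared between arms is a valid randomized contrast. What survives is noise, possible loss of early effect in Jefferson patients, and a within-arm change that cannot be interpreted.

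**Conclusion.** The concern holds in limited form. The plan tests a change from baseline in a score of annual and twice-yearly items, but it defines no look-back for any time point, schedules the baseline review inconsistently, requests no year of records before recruitment, and retrieves month-12 records over different literal lengths by PCP affiliation.

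With care unchanged, window length alone moves the score by about 1.1 to 1.35 of 5 points when two HbA1c tests are required in either window, somewhat less if one test suffices in 6 months, and by 2 to 3 points for a fully adherent participant. Neither calculation applies the due-date rule, which cannot be applied as written. All receipt rates, SDs, the 0.5-point difference, the rate factor of 1.3 and the Jefferson share are assumptions. The probable consequences are an uninterpretable baseline and within-arm change, lower precision, and possible attenuation. This should be corrected before the outcome is scored.

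**What to change.** 1. Reconcile sections 3.2 and 6.9 with section 6.7 and Table 5, so that the baseline chart review for this score is scheduled and assigned.
2. Score every participant on one 12-month window. Baseline is the 12 months ending at randomization; month 12 is randomization to month 12. Using randomization as the boundary leaves no weeks between windows (the section 6.9 steps allow up to 14 + 7 + 7 + 3 = 31 days from index visit to randomization).
3. For Jefferson patients, pool the two checks and assign events to windows by date.
4. Extend the Appendix 12 Epic check and record request back to cover the baseline year, and name the five items there.
5. Count an item as received if it is dated within the window (two tests for HbA1c), replacing the undefined due date.
6. Leave month 6 out of the Aim 2 model for this outcome, or score it on a rolling 12-month look-back and label it as overlapping baseline.
7. Where a signed release does not cover the earlier year, compare the month-12 score between arms, adjusted for the stratification factors.

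The cost is a longer look-back on existing records, a check of what signed releases permit, and loss or relabelling of the month-6 value. No new participant contact is needed for the chart data.
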